12.2 Serious Adverse Event (SAE)

Serious Adverse Event (SAE): A serious adverse event is any problem or unwanted event encountered in a clinical trial or a performance evaluation that has led, could have led, or could lead directly or indirectly to death or to a serious deterioration in the health of a subject or user or any other person, without regard to whether the event was caused by a medical product. (§ 2 no. 5 MPSV). The following events (including laboratory results and outcome events) will be considered to be SAEs and must immediately (within 24 hours) be reported to the study Sponsor by telephone, fax and/or email. These events must be reported whether or not the Investigator believes they are related to study procedures, activities or device:

- Death
- Serious deterioration in the health of the subject, that either resulted in a life threatening illness or injury, or a permanent impairment of a body structure or a body function, or in patient or prolonged hospitalization, medical or surgical intervention to prevent life threatening illness or injury or permanent impairment to a body structure or a body function.
- Malignant Tumor (Austrian Medical Device Act, § 3 Abs.16 MPG as amended)

Serious Adverse Device Effect: An adverse device effect that has resulted in any of the consequences of a Serious Adverse Event.

Note: Planned hospitalization for a pre existing condition, a condition unrelated to the treatment or a procedure required by this study, that is without serious deterioration in health, is not considered a serious adverse event.

12.3 Unanticipated Adverse Device Effect (UADE)

Unanticipated Serious Adverse Device Effect (USADE): Serious adverse device effect which, by its nature, incidence, severity or outcome has not been identified in the risk analysis report.

Anticipated Serious Adverse Device Effect (ASADE): An effect, which by its nature, incidence, severity or outcome has been identified in the risk analysis report. UADEs must be reported to the study Sponsor by telephone, fax and/or email within 24 hours.

12.4 Reporting of Adverse Events

All incidents will be captured as a part of this clinical study. At each contact with the subject, the investigator will seek information on adverse device effects by specific questioning and, as appropriate, by examination. Information on all adverse device effects will be recorded immediately in the source document, and also in the appropriate adverse effect case report form (CRF). All clearly related signs, symptoms, and abnormal diagnostic procedures results should be recorded in the source document. All SAEs, UADEs and

possible device and/or procedure related adverse events must be recorded on the Adverse Event CRF by the Investigator (or his/her designee) and reported to the Sponsor within 24 hours. The report should include: severity, duration, action taken, treatment outcome and relationship to the adverse event to the study device, procedure, concomitant medications, pre existing condition, etc. (i.e., unrelated, relation or relationship unknown).

In the case of serious adverse events (SAE), procedure and/or device failures and malfunctions, medical record documentation (e.g., procedure notes, operative notes, discharge summary, relevant progress notes, imaging or lab studies) must be provided to PQ Bypass or its designee, if requested. All SAEs shall be recorded in the CRF and this information shall be faxed to the Study Monitor/PQ Bypass. If appropriate, PQ Bypass shall inform the Competent Authority and the relevant Ethics Committee about the event within the appropriate timelines.

In accordance with MEDDEV 2.7 / 3 rev.3 (May 2015), the sponsor must report:

- all reportable events as described in section 4 which indicate an imminent risk of death, serious injury, or serious illness and that requires prompt remedial action for other patients/subjects, users or other persons or a new finding to it,
- to the National Competent Authorities where the clinical investigation has commenced,
- Immediately, but not later than 2 calendar days after awareness by sponsor of a new reportable event or of new information in relation with an already reported event.

12.5 Reporting of Device Failures and Malfunctions

All reported device malfunctions or failures of the PQ Bypass Systems are required to be documented in the CRF and must be immediately reported to the study sponsor by telephone, fax and/or within 24 hours. Device failures and malfunctions should also be documented in the subject's medical record. Instructions for returning the investigational device will be provided.

NOTE: Device failures or malfunctions are NOT to be reported as adverse events. However, if there is an adverse event that results from a device failure or malfunction, that specific event would be recorded in the usual way.

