12.6 Documentation, evaluation and notification of Serious Adverse Events

The Investigator shall report all serious adverse events (anticipated or unanticipated) to Sponsor or Sponsor's representative within 24 hours upon becoming aware of events. The Sponsor will ensure compliance with all country specific reporting requirements to the appropriate Ethical Committees and Competent Authorities. SAEs should be reported immediately and no later than 7 days from the Sponsor's first knowledge of the event.

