13.4 Interim Monitoring Visit (ISO 14155)

The monitor shall perform routine on site monitoring visits to verify that

- a) compliance with the CIP, any subsequent amendment(s), this International Standard and regulatory requirements is maintained; deviations shall be discussed with the principal investigator(s) or authorized designee, documented and reported to the sponsor,
- b) only authorized individuals are participating in the clinical investigation,
- c) the investigational device is being used according to the CIP or instructions for use and that, where modifications are required to the device, its method of use or the CIP,

- these are reported to the sponsor,
- d) investigation site resources, including laboratories, equipment and the investigation site team, remain adequate throughout the duration of the clinical investigation,
 - e) the principal investigator continues to have access to an adequate number of subjects and investigational devices,
 - f) signed and dated informed consent forms have been obtained from each subject at the point of enrolment or before any clinical investigation related procedures are undertaken,
 - g) source documents and other clinical investigation records are accurate, complete, up to date, stored and maintained appropriately,
 - h) CRFs and queries are complete, recorded in a timely manner, and consistent with source documents,
 - i) appropriate corrections, additions or deletions are made to the CRFs, dated, explained if necessary and initialed by the principal investigator or by his/her authorized designee; the monitor shall not make corrections, additions or deletions to the CRFs,
 - j) all adverse events and device deficiencies are reported to the sponsor, and all serious adverse events and device deficiencies that could have led to a serious adverse device effect are reported to the sponsor without unjustified delay,
 - k) all serious adverse events and deviations are reported to the EC, if required,
 - l) the storage and investigational device accountability are correct and the traceability process is being followed,
 - m) all other required reports, notifications, applications, submissions and correspondence are maintained in the investigator's files and are accurate, complete, timely, legible, dated and identify the clinical investigation,
 - n) maintenance and calibration of the equipment relevant to the assessment of the clinical investigation is appropriately performed and documented, where applicable,

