upper limit of normal in the absence of new pathological Q waves, (2) post index procedure or endovascular re intervention (≤ 30 days) – CK MB elevation ≥ 3 times the upper limit of normal in the absence of new pathological Q waves, or (3) post Surgical intervention (< 30 days) – CK MB elevation ≥ 5 times the upper limit of normal in the absence of new pathological Q waves.

Post-Procedure ICU Time

Number of hours a patient is in an intensive care unit prior to discharge or moving to a step down or standard care unit.

Primary Assisted Patency

Patency following endovascular re intervention at the target vessel site in case of symptomatic restenosis.

Primary Patency

No significant reduction of flow detectable by Duplex ultrasound (DUS) through the index lesion. Significant reduction of flow was determined as binary restenosis, defined as a peak systolic velocity ratio (PSVR) ≥ 2.5 as measured by DUS.

Post-Procedure Length of Hospital Stay

Number of days from the end of the procedure until the patient is discharged from the hospital. This does not include time spent in a skilled care facility.

Procedure Time

Number of minutes needed to perform the index procedure from time of initial vessel cut down time to time of final guidewire removal. Also referred to as skin to skin time.

Renal Failure

Need for dialysis or a laboratory finding of serum creatinine > 3.5 mg/dL.

Respiratory Failure

The need for mechanical ventilation beyond the first 24 hours post index procedure (and/or re intervention) or the need for re intubation or ventilator support after the first 24 hours (unless the subject was ventilator dependent pre procedure).

Secondary intervention

Any visit to the operating room or catheterization laboratory subsequent to the PQ Bypass Stent Graft implant procedure to treat an adverse event related to the disease, the index procedure or the study device.

Secondary Patency

Patency of the target lesion after treatment of a (re)occlusion of the index lesion.

Serious Adverse Event (SAE)

Any undesirable event occurring which led, could have led or might lead either directly or indirectly to the death or serious deterioration in the health of a subject, user or another person, regardless of whether the event was caused by the medical device.

Stroke or Transient Ischemic Attack (TIA)

- **Stroke** - A new neurological deficit lasting more than 24 hours, or lasting 24 hours or less with a brain imaging study showing infarction.

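### Section 12.5 keeps near-miss device failures off the adverse event record, although Sections 12.2 and 19.0 define them as SAEs

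*Combined protocol and SAP*

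**What the plan says.** **SAE definition.** Section 12.2 covers any problem or unwanted event "that has led, could have led, or could lead directly or indirectly to death or to a serious deterioration in the health", and it applies to participants, users and others alike, whatever the cause. It then lists events to be treated as SAEs: death, serious deterioration (including intervention to prevent serious harm) and malignant tumor. Section 19.0 repeats the broad definition in similar words, again covering events that only had the potential for such harm, and without the list.

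**Device failures.** Section 12.5 requires every malfunction or failure to be documented in the CRF and reported to the sponsor within 24 hours. Its note then says "Device failures or malfunctions are NOT to be reported as adverse events". It makes a single exception, for harm that actually follows: "if there is an adverse event that results from a device failure or malfunction, that specific event would be recorded in the usual way". The opening of Section 12.0, by contrast, lists device failure and malposition among the potential adverse events.

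**Who sees what.** Section 12.4 puts SAEs on the Adverse Event CRF. The Protocol Summary gives the Clinical Events Committee (CEC) the safety endpoints, SAEs and device-related adverse events. Section 13.4, item j, has monitors verify that "device deficiencies that could have led to a serious adverse device effect are reported to the sponsor without unjustified delay". Section 14.4 includes device failures in the DSMB's safety analysis. Appendix III requires SAEs to go to the German authority immediately or quarterly, depending on causality.

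**Time limits to authorities.** Section 12.4 sets a limit for events that indicate imminent risk: "Immediately, but not later than 2 calendar days after awareness by sponsor". Section 12.6 sets a general limit, counted from when the sponsor first learns of the event: "SAEs should be reported immediately and no later than 7 days from the".

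**The concern.** Take a delivery-system failure that is recovered without injury and without any preventive intervention, but that could have caused serious harm. Under 12.2 and 19.0 it is an SAE. Under the 12.5 note it is not reported as an adverse event at all. Two sites could file the same event differently, each following a section of the protocol.

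Classification matters because several downstream steps depend on the SAE label. Section 11.1 names SAE rates associated with the stent graft as a measure of safety. CEC adjudication and the Appendix III reports also start from SAEs. If near misses are filed only as malfunctions, the device-related SAE count is too low by the plan's own definition, and these events get neither adjudication nor a stated route to the authority. In a pre-market study of an implant they are among the more informative early signals.

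**Working it through.** No formula applies and the plan states no figure to reproduce. The check is a comparison of the sections for one test case: a device failure with potential for serious harm, no injury and no intervention to prevent injury.

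| Question | Source | Answer for the test case |
|---|---|---|
| Is it an SAE? | 12.2 opening definition; 19.0 | Yes: potential to cause serious harm is enough |
| Is it on the list of SAEs? | 12.2 bullets | No: no harm and no preventive intervention |
| Is it a possible adverse event? | 12.0 list | Yes: device failure is listed |
| Is it reported as an adverse event? | 12.5 note | No: no adverse event resulted |
| Does the sponsor learn of it? | 12.5 | Yes, within 24 hours |
| Do monitors check it? | 13.4, item j | Yes, for reporting to the sponsor |
| Does the DSMB see it? | 14.4 | Yes, device failures are in its analysis |
| Is it on the Adverse Event CRF? | 12.4 with 12.5 | No, if the 12.5 note is followed |
| Does the CEC adjudicate it? | Protocol Summary | Not unless classed as an SAE or device-related adverse event |
| Does it enter Appendix III reporting? | Appendix III | Triggered by SAEs; no step in Section 12 routes it there |

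**Step 1: site to sponsor.** The limit is 24 hours for SAEs (12.2, 12.4, 12.6) and 24 hours for device failures (12.5). There is no gap here.

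**Step 2: classification.** The 12.5 exception needs an adverse event that results from the failure. The 12.2 and 19.0 definitions do not. Any failure with serious potential and no resulting event falls between them.

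**Step 3: onward from the sponsor.** Nothing in Section 12 says that a failure filed only as a malfunction is screened for SAE status. Section 12.4 also refers to reportable events in section 4 of external guidance. That list is not reproduced, and this protocol's own Section 4.0 is the intended use. Whether the list already covers near misses cannot be settled from the documents.

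**Step 4: the two authority limits.** For an imminent-risk event, 12.4 allows at most 2 calendar days and 12.6 at most 7 days. A report within 2 days meets both, so the stricter limit governs. The only defect is that 12.6, read alone, does not mention the shorter limit.

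**The case against.** The strongest reply is that the 12.5 note expresses a normal convention: the product malfunction is recorded separately from the clinical event it causes. Section 12.1 fits this, since it defines an adverse event by medical occurrence, disease, injury or clinical signs. The class left over is also small, because a failure that needed medical or surgical intervention to prevent serious harm is already on the 12.2 list and its event is recorded in the usual way. Sponsor, monitors and DSMB all have sight of failures, failed devices are returned to the sponsor for analysis (10.2), and 12.6 binds the sponsor to national reporting rules.

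Most of this stands. The convention is reasonable, but it needs an exception where the protocol's own SAE definition reaches the malfunction itself. DSMB review is no substitute for adjudication or authority reporting, since its meeting frequency is still to be determined. The monitor's check ends at the sponsor.

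Two stronger readings are tempting. A reader might infer that near-miss failures escape prompt reporting altogether; the 24-hour rule in 12.5 rules that out. A reader might also infer that 12.6 lets an imminent-risk event wait 7 days. It does not: 12.4 is the specific, mandatory rule for those events, and 12.6 itself asks for immediate reporting.

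**Conclusion.** The conflict between 12.5 and the SAE definition in 12.2 and 19.0 is real and should be corrected. It concerns classification and onward handling: the Adverse Event CRF, SAE counts, CEC adjudication and a stated route into Appendix III. It does not concern whether the sponsor hears of the event.

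The documents give no device failure rate for this study, so the number of affected events cannot be estimated; given the 12.2 list, the class is likely to be small. The primary safety endpoint is TLR, amputation or death at 30 days, which an uninjured near miss does not enter. The primary endpoints, alpha and power are unchanged.

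The conclusion assumes that the opening definition in 12.2 is operative and not cut down by the list after it; Section 19.0, which has no list, supports that. It leaves open whether the external list cited in 12.4 already brings near misses into authority reporting. The time limits in 12.4 and 12.6 need a cross-reference only.

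**What to change.** **Amend the note in 12.5**, for example: *A device failure or malfunction that led, could have led or could lead to death or serious deterioration in health is an SAE as defined in 12.2 and 19.0. It is recorded on the Adverse Event CRF, sent to the CEC and reported under 12.4, 12.6 and Appendix III. Other malfunctions are documented on the malfunction form only.* Add a check-box to the malfunction form so that the site states whether the SAE definition is met.

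**Minor clarification in 12.6:** state that the 2-calendar-day limit in 12.4 governs imminent-risk events.

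The cost is one sentence and a check-box for 12.5, and a cross-reference for 12.6. The reported SAE count may rise slightly, and the report should explain that it includes near misses.

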12.6 Documentation, evaluation and notification of Serious Adverse Events

The Investigator shall report all serious adverse events (anticipated or unanticipated) to Sponsor or Sponsor's representative within 24 hours upon becoming aware of events. The Sponsor will ensure compliance with all country specific reporting requirements to the appropriate Ethical Committees and Competent Authorities. SAEs should be reported immediately and no later than 7 days from the Sponsor's first knowledge of the event.

13.0 MONITORING**13.1 Selection and Qualification of Monitors (ISO 14155)**

Monitors will be appointed by the sponsor. Monitors will be trained with scientific and/or clinical knowledge and the sponsor will document his/her qualifications. The Monitor will be familiar with the investigational product, protocol, consent form and any other written information given to the participant, sponsor's SOPs, and GCP and the relevant regulatory requirements.

13.2 Assessment of the Investigation Site (ISO 14155)

The monitor shall assess each investigation site to verify that the principal investigator has:

- a) adequate qualifications;
- b) adequate resources, including facilities, laboratories, equipment and a qualified investigation site team;
- c) access to an adequate number of subjects.

13.3 Site Initiation (ISO 14155)

The monitor shall initiate each investigation site to ensure that the principal investigator and investigation site team:

- a) have received and understood the requirements and contents of
 - 1) CIP,
 - 2) IB,
 - 3) the informed consent form,
 - 4) CRFs,
 - 5) the instructions for use,
 - 6) any written clinical investigation agreements, as appropriate,
- b) have access to an adequate number of investigational devices,
- c) have been trained in the use of the investigational device, and
- d) are familiar with the responsibilities of the principal investigator

13.4 Interim Monitoring Visit (ISO 14155)

The monitor shall perform routine on site monitoring visits to verify that

- a) compliance with the CIP, any subsequent amendment(s), this International Standard and regulatory requirements is maintained; deviations shall be discussed with the principal investigator(s) or authorized designee, documented and reported to the sponsor,
- b) only authorized individuals are participating in the clinical investigation,
- c) the investigational device is being used according to the CIP or instructions for use and that, where modifications are required to the device, its method of use or the CIP,

- these are reported to the sponsor,
- d) investigation site resources, including laboratories, equipment and the investigation site team, remain adequate throughout the duration of the clinical investigation,
 - e) the principal investigator continues to have access to an adequate number of subjects and investigational devices,
 - f) signed and dated informed consent forms have been obtained from each subject at the point of enrolment or before any clinical investigation related procedures are undertaken,
 - g) source documents and other clinical investigation records are accurate, complete, up to date, stored and maintained appropriately,
 - h) CRFs and queries are complete, recorded in a timely manner, and consistent with source documents,
 - i) appropriate corrections, additions or deletions are made to the CRFs, dated, explained if necessary and initialed by the principal investigator or by his/her authorized designee; the monitor shall not make corrections, additions or deletions to the CRFs,
 - j) all adverse events and device deficiencies are reported to the sponsor, and all serious adverse events and device deficiencies that could have led to a serious adverse device effect are reported to the sponsor without unjustified delay,
 - k) all serious adverse events and deviations are reported to the EC, if required,
 - l) the storage and investigational device accountability are correct and the traceability process is being followed,
 - m) all other required reports, notifications, applications, submissions and correspondence are maintained in the investigator's files and are accurate, complete, timely, legible, dated and identify the clinical investigation,
 - n) maintenance and calibration of the equipment relevant to the assessment of the clinical investigation is appropriately performed and documented, where applicable,
 - o) current laboratory normal values, laboratory certifications, accreditations, or other validations are present in the investigator's file, if required,
 - p) subject withdrawal has been documented; the monitor shall discuss this with the principal investigator or his/her authorized designee,
 - q) subject non compliance with the requirements stated in the informed consent has been documented; the monitor shall discuss this with the principal investigator or his/her authorized designee,
 - r) the principal investigator and investigation site team are informed and knowledgeable of all relevant document updates concerning the clinical investigation, and
 - s) any corrective and preventive actions, as needed, have been implemented and are effective.

